10.1.4 DOSE PRESENTATION

Doses of RA101495 will be determined by a target dose and weight, accomplished using a fixed dose by weight brackets. These brackets are grouped by bodyweight category such that each subject will receive the no less than the target minimum dose to avoid sub-therapeutic dosing. For the 0.1 mg/kg dose, subjects will receive, at a minimum, a fixed dose of 0.1 mg/kg (range 0.10 to 0.14 mg/kg); in the 0.3 mg/kg dose, subjects will receive a minimum dose of 0.3 mg/kg (range 0.3 mg/kg to 0.41 mg/kg). Table 3 summarizes dose presentations for RA101495 0.1 mg/kg and 0.3 mg/kg doses. Subjects who present with a higher body weight (>109 kg) will be accommodated on a case-by-case basis, in consultation with the medical monitor.

Table 3 Dose Presentations by Weight Brackets

Target Dose (mg/kg)	Dose Presentation			Weight Range (kg)	Dose Range (mg/kg)
	Fill Volume		Dose		
	Number	mL	mg		
0.1	1	0.150	6	≥43 to <61	0.10 to 0.14
0.1	2	0.220	8.8	≥61 to <88	0.10 to 0.14
0.1	3	0.310	12.4	≥88 to <109	0.11 to 0.14
0.3	4	0.416	16.6	≥43 to <56	0.30 to 0.39
0.3	5	0.574	23	≥56 to <77	0.30 to 0.41
0.3	6	0.810	32.4	≥77 to <109	0.30 to 0.42

10.1.4.1 MISSED DOSES

If a subject misses one dose (i.e. 1 day) of RA101495, the subject should document the missed dose in his/her subject e-diary and take the next planned dose as scheduled. The subject should contact the investigator as soon as possible. If a subject misses 2 or more doses, the subject must notify the investigator immediately.

10.2 STUDY TREATMENT MANAGEMENT

10.2.1 PREPARATION AND DISPENSING

Pre-filled syringes will be dispensed to each subject every 2 weeks, beginning on Day 1 of the Treatment Period.

Subjects will be trained and provided detailed instructions regarding administration of RA101495 using the pre-filled syringes and the injection device in a separate manual.

10.2.2 STUDY DRUG SUPPLY, STORAGE, AND HANDLING

RA101495 will be provided as a sterile, preservative-free, aqueous solution for injection containing 40 mg/mL of active ingredient, RA101495, in a formulation of 50 mM sodium

phosphate and 76 mM sodium chloride at a pH of 7.0 pre-filled into a 1 mL glass syringe with a ½ inch, 29 gauge staked needle. Six dosage strengths will be supplied as shown in Table 3.

The IMP should be stored at 2 °C to 8°C.at the study site. Once dispensed to subjects, the IMP may be stored at room temperature (20°C to 25°C [68°F to 77°F]) for up to 30 days protected from sources of heat, light and damage. Storage of IMP outside of room temperature should be avoided.

Subjects will be instructed to self-inject SC doses daily every 24 hours at approximately the same time each day. The subject will be provided with an injection device for use during the study. Subject may inject in the abdomen (preferred site), thigh or upper arm.

All subjects will receive a study drug kit that will include RA101495 prefilled syringes, a syringe disposal container, alcohol wipes, and adhesive dressings.

10.2.3 DISPOSAL, RETURN, OR RETENTION OF UNUSED DRUG

At all visits, subjects will also receive a secure container to dispose of used syringes while at home. At each visit the subject should return the used container containing all used syringes to the site. The unused study drug (unused syringes) should be retained by the subject and be used first in the immediate two weeks.

All study drug (syringes) and disposal containers must be returned to the site at the last study visit.

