5 TIME AND EVENTS TABLE

Assessments to be performed during the study are shown in Table 1.

Table 1 Time and Events Table

Phase	Screening Period	Treatment Period								
		0	1	2	3	4	6	8	10	12 (End of Study)
Study Week →	-8 to 1	0	1	2	3	4	6	8	10	12 (End of Study)
Study Day ^a →	-56 to -1	1 ± 2 ^b	8 ± 2	15 ± 2	22 ± 2	29 ± 2	43 ± 4	57 ± 4	71 ± 4	84 ± 4
Study Procedure ↓										
ICF process and signed ICF	X									
Review eligibility criteria	X	X								
Medical history and demographics	X									
Prior and concomitant medications	X	X	X	X	X	X	X	X	X	X
Physical examination	X	X				X				X
Height and weight ^c	X	X				X				X
Vital signs	X	X				X				X
Electrocardiogram	X	X				X				X
Neisseria throat swab ^d	X									
Neisseria vaccination ^d		X				X				
Ciprofloxacin treatment ^d		X	X	D14						
Blood chemistry ^e	X	X	X	X	X	X	X	X	X	X
Hematology	X	X	X	X	X	X	X	X	X	X
Coagulation ^f	X	X	X	X	X	X	X	X	X	X
Urinalysis	X	X	X	X	X	X	X	X	X	X
PNH clone size	X					X		X		X
Pregnancy test ^g	X	X				X		X		X
Adverse events		X	X	X	X	X	X	X	X	X

Phase	Screening Period	Treatment Period								
		0	1	2	3	4	6	8	10	12 (End of Study)
Study Week →	-8 to 1	0	1	2	3	4	6	8	10	12 (End of Study)
Study Day^a →	-56 to -1	1 ± 2^b	8 ± 2	15 ± 2	22 ± 2	29 ± 2	43 ± 4	57 ± 4	71 ± 4	84 ± 4
Assessment of injection site reactions ^h		X	X	X	X	X	X	X	X	X
Pharmacokinetics RA101495 ⁱ		X	X	X	X	X	X	X	X	X
Pharmacokinetics eculizumabi	X	X		X		X	X			
Pharmacodynamics RA101495 ⁱ		X	X	X	X	X	X	X	X	X
Anti-drug antibody ^k		X ^k				X		X		X
Quality of life questionnaires										
EORTC-QLQ-C30		X				X		X		X
FACIT-Fatigue		X				X		X		X
EQ-5D		X				X		X		X
Treatment satisfaction assessment										X
Additional biomarker samples ⁱ		X	X	X	X	X	X	X	X	X
Pharmacogenomic analysis (optional) ^l		X ^l								
Electronic diary training and dispensation, collection at End of Study		X								X
RA101495 administration ^m		X	X	X	X	X	X	X	X	X
RA101495 dispensing and return ⁿ		X		X		X	X	X	X	X

Abbreviations: EORTC-QLQ-C30=European Organization for Research and Treatment of Cancer-Quality of Life Questionnaire; EQ-5D=EuroQoL 5D questionnaire; FACIT-F=Functional Assessment of Chronic Illness Therapy-Fatigue Scale; ICF=informed consent form; LDH=lactate dehydrogenase; NA=not applicable; PD=pharmacodynamic; PK=pharmacokinetic.

- a. Study visits have a Visit window of ± 2 days after the actual planned Visit day for the first 4 weeks, and ± 4 days from week 6 to week 12.

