- n. Prefilled syringes containing RA101495 will be dispensed every 2 weeks. Subjects will also receive a secure container to dispose of used syringes at each visit and should return the used container containing all used syringes to each study visit. All study drug (syringes) and disposal containers must be returned to the site at the last study visit. Dosing on study visit days will be held until the completion of the PK and PD sample blood collection has been completed.

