10.1.2.1 DOSE ESCALATION

From the Week 2 Visit onwards, if a subject has not achieved an adequate response (defined as an LDH $<1.5 \times$ ULN), and following evaluation of safety and tolerability data by the treating investigator and the medical monitor, the dose should be escalated to 0.3 mg/kg daily. The dose may also be escalated to 0.3 mg/kg daily at any time in the event of an overt breakthrough hemolysis event (e.g. hemoglobinuria).

For subjects who have a dose increase to 0.3 mg/kg, samples for PK and PD should be collected at pre-dose of the first day of the new dose, then at scheduled visits per the Time and Events Table (Table 1).

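### Protocol 10.2.3 has leftover syringes used first whatever their strength, and nothing requires the 0.1 mg/kg syringes to be returned when the dose is escalated to 0.3 mg/kg

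*Protocol*

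**What the plan says.** **Leftover drug.** Protocol 10.2.3 states: "The unused study drug (unused syringes) should be retained by the subject and be used first in the immediate two weeks". It mentions neither strength nor a change of dose.

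**Escalation.** Under Protocol 10.1.2.1, a subject whose LDH is not below 1.5 x ULN from Week 2 on is reviewed by the investigator and the medical monitor, and "the dose should be escalated to 0.3 mg/kg daily". The section adds: "The dose may also be escalated to 0.3 mg/kg daily at any time in the event of an overt breakthrough hemolysis event". The only practical step it attaches to the change is that "samples for PK and PD should be collected at pre-dose of the first day of the new dose".

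**Dose per syringe.** Protocol 10.2.2 and Table 3 (10.1.4) describe six fixed fills at 40 mg/mL, three for each dose level. Section 10.1.4 sets a floor: "in the 0.3 mg/kg dose, subjects will receive a minimum dose of 0.3 mg/kg".

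**Return of drug.** Table 1 has a row "RA101495 dispensing and return", marked at Weeks 0, 2, 4, 6, 8, 10 and 12. Its footnote n says that subjects "should return the used container containing all used syringes to each study visit", and then: "All study drug (syringes) and disposal containers must be returned to the site at the last study visit". Sections 8.4.1 and 8.4.2 also require unused syringes back at early discontinuation and at withdrawal. SAP 3.7 repeats the used-container and last-visit rules.

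**The concern.** A subject cannot adjust the dose within a syringe, so an instruction about which syringe to use first is in effect an instruction about dose. After escalation, a subject who still holds 0.1 mg/kg syringes and follows 10.2.3 to the letter would take the superseded dose until they are gone.

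These are the subjects for whom the starting dose was judged insufficient, or who had overt breakthrough hemolysis. The protocol treats under-dosing as important: 8.1.1 stresses avoiding sub-therapeutic doses, and 6.5.1 warns that even a short, modest loss of complement blockade can bring on breakthrough hemolysis.

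The slip might also go unseen. Subjects inject at home. The e-diary items in 10.3 and 11.5 are date, time and injection location, and 10.2.4 counts syringes dispensed, used and returned. Strength is not among the items described.

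**Working it through.** The plan states no figure for this point. The check has two parts: the dose in a leftover syringe, and the occasions on which unused drug must come back.

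**1. Table 3 fills.** Dose = fill volume x 40 mg/mL (10.2.2).

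- 0.1 mg/kg level: 0.150 x 40 = 6.0 mg; 0.220 x 40 = 8.8 mg; 0.310 x 40 = 12.4 mg.
- 0.3 mg/kg level: 0.416 x 40 = 16.64 mg (table: 16.6); 0.574 x 40 = 22.96 mg (table: 23); 0.810 x 40 = 32.4 mg.

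The table agrees with the concentration.

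**2. Share of the assigned dose in one leftover syringe.** The two levels use different weight brackets, so the ratio is taken in each overlapping band. Share = 0.1 mg/kg fill / 0.3 mg/kg fill. Dose per kg = 0.1 mg/kg fill / weight at each end of the band.

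| Weight (kg) | Leftover / assigned (mg) | Share | Leftover dose (mg/kg) |
|---|---|---|---|
| 43 to <56 | 6 / 16.6 | 0.361 | 0.107 to 0.140 |
| 56 to <61 | 6 / 23 | 0.261 | 0.098 to 0.107 |
| 61 to <77 | 8.8 / 23 | 0.383 | 0.114 to 0.144 |
| 77 to <88 | 8.8 / 32.4 | 0.272 | 0.100 to 0.114 |
| 88 to <109 | 12.4 / 32.4 | 0.383 | 0.114 to 0.141 |

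The share runs from 26% to 38%. The dose delivered is about 0.10-0.14 mg/kg, against the 0.3 mg/kg minimum in 10.1.4. Heavier subjects are handled case by case and are not covered by this table.

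**3. When unused drug must be returned.**

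| Occasion | Unused syringes returned? | Source |
|---|---|---|
| Ordinary visit | No: used-syringe container only; unused kept | 10.2.3; Table 1, footnote n |
| Last study visit | Yes | 10.2.3; Table 1, footnote n; SAP 3.7 |
| Early discontinuation | Yes | 8.4.1 |
| Withdrawal | Yes | 8.4.2 |
| Escalation to 0.3 mg/kg | Not stated | 10.1.2.1 |

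The word return in the Table 1 row does not fill the gap, because footnote n explains it as used containers until the last visit.

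**4. Side by side.** Sections 10.1.2.1 and 10.1.4 put an escalated subject on at least 0.3 mg/kg. Section 10.2.3 tells the same subject to use the syringes in hand first. If those are 0.1 mg/kg syringes, both instructions cannot be followed.

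**The case against.** The strongest reply is that the dosing sections set the dose and 10.2.3 only covers storage and return. Section 10.1.1 ties each injection to the dose requirement, 10.1.3 has subjects inject whichever daily dose applies to them, and 10.1.4 sets the floor. Taken as a whole, the protocol gives the right dose. The sentence in 10.2.3 also reads naturally as stock rotation: 10.2.2 allows 30 days at room temperature, dispensing is every two weeks, and using carry-over in the next two weeks keeps a syringe to about 28 days. Same-strength syringes were probably meant.

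There are practical safeguards too. The investigator and medical monitor review LDH-driven escalations, syringes are counted, the e-diary is monitored, and nothing forbids an earlier return or an unscheduled supply. Section 10.2.1 mentions a separate manual, not among the documents, that may cover the change of strength.

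Most of this stands. It shows what was probably intended and makes the literal reading less likely in practice. It does not change the text: 10.2.3 is the written rule on leftovers, it has no limit by strength, and the subject follows it at home. The safeguards described do not record strength.

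A reader might go further and infer a definite delay, by counting days from an escalation to the next dispensing visit. The documents do not support this. Such a count reflects the dispensing calendar and assumes no off-schedule supply. Yet 10.1.2.1 allows escalation at any time and foresees a blood sample before the first new dose, an occasion at which syringes could be exchanged.

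**Conclusion.** The point holds as a minor dosing-safety correction. Taken literally, the retention rule conflicts with the escalation order and the minimum dose, and no return rule for superseded syringes removes the conflict.

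Its size can be given per syringe only: 26-38% of the assigned fixed dose. This assumes the Table 3 fills and one syringe per daily dose. How many 0.1 mg/kg syringes a subject would hold at escalation is not given, nor is how often sites would apply the rule literally, so no number of affected doses or subjects follows.

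A reader might also infer damage to the primary result. The documents give no basis for that. The sample-size figures in Protocol 13.1 rest on assumed LDH means, standard deviations and correlations, which do not involve syringe handling. The planned primary analysis in SAP 3.9.1 averages the scheduled Week 6-12 LDH values whatever dose level the subject is on. Sample size, power and that analysis stand as written.

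**What to change.** Make two changes to the protocol wording.

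- **10.2.3:** limit retention and first use to syringes of the strength currently assigned to the subject.
- **10.1.2.1:** state that on the first day of the new dose, when the pre-dose PK and PD samples are taken, the subject is supplied with 0.3 mg/kg syringes, and all remaining 0.1 mg/kg syringes are returned and not used.

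The first change removes the conflict. The second takes the superseded strength out of the home and ties the exchange to a contact the protocol already requires.

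The cost is a few discarded 0.1 mg/kg syringes per escalated subject and possibly an unscheduled supply of the higher strength. No extra subjects and no SAP change are needed.

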10.2.4 DRUG ACCOUNTABILITY

An e-diary where the subject documents study drug administration will be used to reconcile accountability during the study. The number of study drug syringes dispensed used, and returned will be documented.

10.3 COMPLIANCE

Subjects will be required to record the date, time, and location of injections each day in an e-diary. The e-diary entries will be evaluated to determine compliance with study drug administration. If a subject does not confirm daily dosing using the e-diary, the investigator will receive an automated notification to contact the subject.

11 STUDY ASSESSMENTS

Please refer to Table 1 for the timing of study assessments.

11.1 SUBJECT AND BASELINE DISEASE CHARACTERISTICS

11.1.1 DEMOGRAPHIC DATA

The following demographic data will be collected: date of birth, gender, ethnicity, and race.

11.1.2 DISEASE AND PRIOR TREATMENT HISTORY

A detailed history of PNH for a minimum of 6 months prior to Screening will be obtained, including (but not limited to) the following data: date of diagnosis, PNH clone size at diagnosis (if available), history of thrombotic events, history of transfusions, and history of PNH-specific prior therapy (e.g. immunosuppressives, anticoagulants, associated bone-marrow disorders).

For Cohort B (Switch) subjects, the date ecilizumab treatment was initiated and dose received will be documented. A dosing history for each subject (including dates and all dosage changes for a minimum of 6 months prior to Screening) will also be recorded.

11.1.3 PRIOR AND CONCOMITANT MEDICATIONS

In addition to PNH-specific prior therapy (Section 11.1.2), all prescriptions and over-the-counter medications taken during the 30 days prior to the screening visit will be documented.

Concomitant medications include any prescription or over-the-counter medication that is ongoing on Day 1 or that is initiated following the first dose of study drug on Day 1.

Findings will be recorded on the subject's source documents and entered on the appropriate eCRF. Any changes to concomitant medications during the Treatment Period will be recorded in the eCRF.

11.2 SAFETY ASSESSMENTS

11.2.1 MEDICAL AND SURGICAL HISTORY

Relevant medical history will be documented to assess subject eligibility.

Detailed medical history regarding the occurrence of specific events or conditions (e.g. underlying bone marrow pathology, major vascular events, pulmonary hypertension, impaired renal or hepatic function, infections, malignancies) for a minimum of 6 months prior to Screening will also be collected.

11.2.2 PHYSICAL EXAMINATION

Physical examinations will include the following assessments:

- General inspection
- Weight (kg) and height (height in cm to be collected at Screening
- Visit only)
- Examination of the injection site and draining nodes
- Head/ears/eyes/nose/throat examination
- Mucosal examination for icterus
- Cardiac examination
- Auscultation of lungs
- Abdominal examination (liver, spleen, and lower abdomen)
- Assessment for neurological deficits
- Musculoskeletal assessment

Any abnormalities found will be recorded in the eCRF.

11.2.3 VITAL SIGNS

Vital signs (heart rate, body temperature, and blood pressure) will be measured in the sitting position after resting for at least 5 minutes. If blood samples are scheduled at the same time, vital signs should be measured before the blood draw. Blood pressure may be measured manually or by automated device, preferably in the non-dominant arm. The same measurement technique should be used throughout the study for all subjects. Temperature will be measured with an electronic device.

11.2.4 ELECTROCARDIOGRAM

Subjects should be in a supine position (lying down) for at least 5 minutes prior to and during the 12-lead ECG recording. ECGs will be assessed as normal or abnormal by the investigator; any abnormal findings will be described in the eCRF and the investigator will assess clinical significance. The ECG recording strip will be signed and dated by the investigator and stored in the medical records.

ECGs should be performed prior to blood draws when both assessments are completed (see Table 1).

11.2.5 NEISSERIA MENINGITIDIS TESTING

All subjects must have a negative result for *Neisseria meningitidis* colonization via a throat swab prior to study entry. The throat swabs for *Neisseria meningitidis* will be obtained at Screening and sent to a certified laboratory for analysis to confirm absence of colonization.

11.2.5.1 NEISSERIA MENINGITIDIS PROPHYLACTIC TREATMENT

All subjects who have not been previously vaccinated will receive prophylactic treatment with *Neisseria meningitidis* vaccine and ciprofloxacin. These subjects must be vaccinated against *Neisseria meningitidis* prior to starting their first dose of RA101495. A booster vaccination should be administered as clinically indicated, consistent with local standard of care. All previously unvaccinated subjects will be treated with oral ciprofloxacin from Day 1 to Day 14. All Cohort B (Switch) subjects must have documentation of prior *Neisseria meningitidis* vaccination (and booster if appropriate) prior to study entry.

11.2.6 ADVERSE EVENT RECORDING

Guidance on the identification, monitoring, and reporting of AEs is provided in Section 12.

11.2.7 LABORATORY SAFETY ASSESSMENTS

11.2.7.1 BLOOD CHEMISTRY AND HEMATOLOGY

Clinical chemistry and hematology analytes to be collected are identified in Table 4 and should be performed as specified in the Time and Events Table 1. All coagulation tests should be performed as per standard practice on any subject taking anticoagulant therapy in addition to specified assessments in this schedule of events.

Table 4 Clinical Chemistry, Hematology, and Coagulation Analytes

Clinical Chemistry	Hematology
alanine aminotransferase (ALT)	free hemoglobin
albumin	haptoglobin
alkaline phosphatase (ALP)	hematocrit
amylase	hemoglobin
aspartate aminotransferase (AST)	mean corpuscular hemoglobin (MCH)
bicarbonate	mean corpuscular hemoglobin concentration (MCHC)
bile acids	mean corpuscular volume (MCV)
bilirubin (total, direct, and indirect)	platelet count
blood urea nitrogen (BUN)	RBC count
calcium	reticulocyte count
chloride	white blood cell (WBC) count and differential (%)
creatinine	Coagulation
gamma-glutamyl transferase (GGT)	international normalized ratio (INR)/prothrombin time (PT)
glucose	fibrinogen
lactate dehydrogenase (LDH)	partial thromboplastin time (PTT) or activated partial thromboplastin time (aPTT or APTT)
lipase	Other
potassium	C-reactive protein (CRP)
sodium	creatine phosphokinase (CPK)
total protein	
uric acid	

11.2.7.2 URINALYSIS

A urinalysis will be performed to measure pH, specific gravity, protein (qualitative), glucose (qualitative), ketones (qualitative), bilirubin (qualitative), urobilinogen, occult blood, hemoglobin, and cells. A microscopic examination will be performed, if necessary. Hemoglobinuria will be assessed using a urine colorimetric scoring system.

11.2.7.3 PREGNANCY TEST

A serum pregnancy test for human chorionic gonadotropin will be performed on female subjects of childbearing potential at Screening.

A urine dipstick pregnancy test (human chorionic gonadotropin) will be performed on female subjects of childbearing potential at Day 1 pre-dose and Day 29, Day 57, and Day 84 (End of Study).

11.2.8 PNH CLONE

Blood sample for measurement of PNH clone size will be collected at Screening and Day 29, Day 57, and Day 84 (or End-of-Study Visit). PNH clone size will be determined by peripheral blood flow cytometry analysis (RBCs and granulocytes).

11.2.9 IMMUNOGENICITY

Blood samples for ADAs will be collected prior to dosing on Day 1 and on Day 29, Day 57, and Day 84 (or at the End-of-Study Visit) in all enrolled subjects. Samples will be sent to a central laboratory to determine the presence or absence of antibodies against RA101495 using a validated assay.

Detailed instructions regarding sample collection, processing, and shipping will be provided in a separate laboratory manual.

11.3 EFFICACY ASSESSMENTS

Efficacy assessments include the measurement of serum LDH levels as a measure of intravascular hemolysis. Additional assessments will include laboratory assessments of total bilirubin, total hemoglobin, free hemoglobin, haptoglobin, reticulocytes, and hemoglobinuria.

11.4 PHARMACOKINETIC AND PHARMACODYNAMIC ASSESSMENTS

Blood samples for the measurement of plasma concentrations of RA101495 and metabolites will be collected on all subjects. Subjects in Cohort B will also have a blood sample for measurement of eculizumab plasma concentrations.

Blood samples for pharmacodynamic assessments will be collected from all subjects and include measurements of:

- CH₅₀
- sRBC lysis for classical complement pathway
- Wieslab ELISA for alternative complement pathway
- C5 levels

Blood samples for PK and PD will be collected at the following time points in relationship to the first dose of RA101495: pre-dose (within 1 hour before first dose administration) and at 1, 3, and 6 hours post-dose on Day 1. For subjects who have a dose increase to 0.3 mg/kg, samples for PK and PD should be collected at pre-dose Day 1 of the new dose.

For subjects in Cohort B only, blood samples for PK of eculizumab should be collected at screening, Day 1, Day 15, Day 29, and Day 43. The sample should be collected prior to administration of RA101495.

All samples will be sent to a central laboratory for analysis. Detailed instructions regarding PK and PD sample collection, processing, and shipping will be provided in a separate laboratory manual.

